### **Months 10 and Month 11 ( $\pm$ 10 days)**

- Collect blood samples for the following assessments (at approximately the same time that this was done at baseline):
  - Hematology
  - Labile plasma iron
  - Transferrin saturation
  - Serum ferritin
  - C-reactive protein

**Notes:**

- A patient whose SF level is found to be  $\geq 1000 \mu\text{g}/\text{L}$  at 2 consecutive visits is to be withdrawn; however, since SF level may be impacted by the presence of infection, it must additionally be verified that the child has had no signs of infection in the previous 7 days, including the day of the visit, and that the level of CRP is no greater than 20% higher than the normal range for the patient's age. If there are signs of infection and/or the CRP level is above this threshold, an SF level  $\geq 1000 \mu\text{g}/\text{L}$  must be checked again a minimum of a week later before the patient's study status can be determined. (If an investigator has valid reason to believe that an SF level  $\geq 1000 \mu\text{g}/\text{L}$  may be attributable to infection even if this is not indicated by the CRP result, SF may be rechecked once more a minimum of one week later.)
- If a transfusion is scheduled on the day of the visit, the blood samples for serum ferritin, LPI, and TSAT must be collected before the transfusion is performed.
- Measure vital signs (heart rate, blood pressure, and body temperature)
- Measure weight and height/length
- Review and update transfusion history
- Ask the parent/guardian (and patient, if applicable) about any adverse events that have occurred and concomitant medications that have been taken since the last site visit
- Additionally review the diary card for information on adverse events and use of concomitant medications, and file the diary card with the source documents
- Collect study medication containers, and check them in order to calculate treatment compliance
- Check the laboratory results from the previous 3 visits (Months 7, 8, and 9 *or* Months 8, 9, and 10) to verify whether:
  - The patient has had an SF value  $\geq 800 \mu\text{g}/\text{L}$  (but still below 1000  $\mu\text{g}/\text{L}$ ) and/or an LPI value  $\geq 0.6 \mu\text{M}$  and/or a TSAT value  $\geq 60\%$  at 2 consecutive visits, **or**
  - An increasing trend in any of the above 3 measures at 3 consecutive visits, regardless of value

If none of these criteria are met, the dosage is to remain at 50 mg/kg/day; if any of them are met, the dosage is to be increased to 75 mg/kg/day.

- Dispense enough study medication to last until the next scheduled visit, with an allowance for the visit window of  $\pm$  10 days, along with a reminder if necessary on how to administer it
- Administer the morning dose of study medication
- Provide the parent/guardian (or patient, if applicable) with a new diary card, along with a reminder if necessary about how to complete it
- Instruct parent/guardian (and patient, if applicable) to do the following:
  - Bring the patient to either the study site or a local laboratory for a biweekly blood draw
  - In the event of any symptoms indicative of infection such as fever, sore throat, or flu-like symptoms, immediately interrupt therapy and contact the clinic
  - At the next site visit, bring back the completed diary card plus all medication containers, whether empty, partly used, or unopened
  - In the event of a decision to withdraw from the study before completion, bring the patient to the clinic for an Early Termination visit as soon as possible, and no later than one month following the last dose of study medication
- Schedule next study visit, and instruct the parent/guardian that: 1) on the preceding day, the evening dose of study medication must be administered at least 12 hours before the start of the visit, and 2) on the day of the visit, the morning dose must not be taken beforehand; it will be administered at the site.

As soon as the SF results from this visit are available, check to see if the SF level was  $\geq$  1000  $\mu$ g/L (taking the factor of possible infection into account, as described above) at **both this and the previous visit**. If no, have the patient continue; if yes, immediately terminate the patient from the study and schedule an early termination visit.

### **Month 12 ( $\pm$ 10 days) (End of Study Visit)**

**Note:** A study staff member is to call the patient's home prior to this visit with a reminder to not administer the morning dose before coming to the site.

- Collect blood samples for the following assessments (at approximately the same time that this was done at baseline):
  - Hematology
  - Blood chemistry
  - Prolactin (pre-dose sample)

- Labile plasma iron
- Transferrin saturation
- Serum ferritin
- C-reactive protein

**Notes:**

- Since SF level may be impacted by the presence of infection, it must additionally be verified that the child has had no signs of infection in the previous 7 days, including the day of the visit, and that the level of CRP is no greater than 20% higher than the normal range for the patient's age. . . If there are signs of infection and/or the CRP level is above this threshold, an SF level  $\geq 1000 \mu\text{g/L}$  must be checked again a minimum of a week later. (If an investigator has valid reason to believe that an SF level  $\geq 1000 \mu\text{g/L}$  may be attributable to infection even if this is not indicated by the CRP result, SF may be rechecked once more a minimum of one week later.)
- If a transfusion is scheduled on the day of the visit, the blood samples for serum ferritin, LPI, and TSAT must be collected before the transfusion is performed.
- Collect a urine specimen for urinalysis
- Perform a physical examination (to be completed by the investigator or a qualified delegate)
- Measure vital signs (heart rate, blood pressure, and body temperature)
- Measure weight and height/length
- Review and update transfusion history
- Ask about any adverse events that have occurred and concomitant medications that have been taken since the last site visit
- Additionally review the diary card for information on adverse events and use of concomitant medications, and file the diary card with the source documents
- Collect study medication containers, and check them to calculate treatment compliance
- Administer the final dose of study medication, ensuring that this is done at approximately the same time as at baseline, and note the exact time at which it is given
- Collect a blood sample for the assessment of prolactin at 1.5 hours ( $\pm 5 \text{ min}$ ) post-dose

### **Early termination visit (if applicable)**

From Month 2 to Month 11, a patient who is determined to have had a serum ferritin level  $\geq 1000 \mu\text{g/L}$  at 2 consecutive visits will be terminated from the study, and is to return for an early termination visit as soon as possible. The following procedures will be done:

- Collect blood samples for hematology and blood chemistry assessments
- Collect a urine specimen for urinalysis
- Perform a physical examination (to be completed by the investigator or a qualified delegate)
- Measure vital signs (heart rate, blood pressure, and body temperature)
- Measure weight and height/length
- Review and update transfusion history
- Ask about any adverse events that have occurred and concomitant medications that have been taken since the last site visit
- Additionally review the diary card for information on adverse events and use of concomitant medications, and file the diary card with the source documents
- Collect study medication containers, and check them to calculate treatment compliance

For patients who withdraw early for reasons other than reaching the serum ferritin threshold, the early termination visit will include all procedures done at the Month 12 visit except for measurement of prolactin.

Participation in the study is now complete. Patients whose SF level is still below  $1000 \mu\text{g/L}$  at 12 months will be offered participation in an extension study, LA55-EXT, in which they will continue to receive their assigned study product for up to 2 more years. Patients who are terminated early because they have already reached the  $1000 \mu\text{g/L}$  threshold will not be eligible to enroll in the extension study.

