#### 4.5 Patient Withdrawal

Patients/parents have the right to withdraw/withdraw their child from the study at any time and for any reason without consequence to future care by the investigator or study center.

A patient may be withdrawn from the study at any time, at the discretion of the investigator, for any of the following reasons:

- Medical or safety reasons considered significant by the parent/legal guardian (or patient, if applicable) and/or the investigator
- Requirement for concomitant medication that might interfere with the evaluation of study treatment or may be contraindicated
- Occurrence of other illnesses that might affect the patient's further participation in the study or evaluation of study treatment
- A protocol deviation that might interfere with study assessments, as judged by the investigator
- Repetitive non-compliance with the protocol or with instructions of the investigator
- Participation in another clinical trial at any time during the conduct of this study
- Any other situation where, in the opinion of the investigator, continuation of the study would not be in the best interest of the patient

A patient **must** be withdrawn from the study if any of the following conditions apply:

- Attainment of a serum ferritin level  $\geq 1000 \mu\text{g/L}$  at 2 consecutive visits (provided that the child has had no signs of infection in the previous 7 days and that CRP level is not greater than 20% higher than the normal range for the patient's age)
- Occurrence of moderate neutropenia or of severe neutropenia/agranulocytosis (see [Section 7.2.1.8.1](#))
- Occurrence of any adverse event characterized as life-threatening or disabling that is not associated with the patient's condition

- Receipt of a rescue medication (see [Section 4.7](#))
- Termination of the study by the sponsor

Parents/legal guardians who decide to withdraw their child from the study (or, in the case of a child who is able to communicate this, a patient who wishes to withdraw) should always be contacted, if possible, in order to ask about the reason for withdrawal, whether any adverse events (AEs) occurred, and use of concomitant medications. A withdrawn patient should return for an Early Termination visit. All investigational product and materials should be returned. If any AEs occurred, the investigator must attempt to follow up on the outcome until resolution or for 30 days post-termination, whichever comes first.

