#### **4.5.2 Treatment Interruptions**

Study medication will be interrupted for ANY of the following reasons:

- If a patient develops fever ( $\geq 38.0^{\circ}\text{C}$ ) or any sign of infection during the study, deferiprone must be interrupted immediately, and neutrophil count should be obtained and monitored more frequently; every 2 days if  $\text{ANC} < 1.5 \times 10^9/\text{L}$ . Therapy with deferiprone can be re-initiated once all symptoms have been resolved, if the  $\text{ANC}$  is  $\geq 1.5 \times 10^9/\text{L}$ .
- Parents/guardians (and patients if applicable) are to be advised to immediately report any symptoms indicative of infection such as fever, sore throat, and flu-like symptoms. Participants will be provided with a thermometer, and will be instructed to seek immediate medical attention at a hospital or clinic if the patient experiences fever ( $\text{temperature} \geq 38.0^{\circ}\text{C}/100.4^{\circ}\text{F}$ ). Body temperature may be measured at the ear, axilla, or mouth. In presence of confirmed fever and/or infection, patients will be required to have their neutrophil counts tested as soon as possible and no later than 24 hours after the symptoms of infection are detected. Therapy with study drug can be re-initiated once all symptoms have been resolved and it is deemed safe by the investigator.
- If a patient develops mild neutropenia during the study ( $\text{ANC} < 1.5 \times 10^9/\text{L}$  but  $\geq 1.0 \times 10^9/\text{L}$ ; see [Section 7.2.1.8.1](#)), therapy must be interrupted immediately, and neutrophil count must be obtained and monitored every 2 days. Therapy can be re-initiated once

two successive ANCs are  $\geq 1.5 \times 10^9/L$  and it is deemed safe by the investigator. If the ANC is still  $< 1.5 \times 10^9/L$  after 14 days, the patient will be withdrawn from the study.

- A patient who develops neutropenia that is defined as moderate (ANC  $< 1.0 \times 10^9/L$ ) or severe (ANC  $< 0.5 \times 10^9/L$ ) is to be immediately withdrawn from the study.

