**Table 5.1 Table of study procedures**

	Day -14 to 0 (Screening)	Month 0, Day 0 (Baseline)	Month 1 	Month 2	Month 3	Month 4	Month 5	Month 6	Month 7	Month 8	Month 9	Month 10	Month 11	Month 12 or End of Study 
Informed consent/ assent	X													
Demographics	X													
Medical history	X													
Eligibility criteria	X	V												
Randomization		X												
Hematology 	X	X	Weekly ( $\pm 3$ days) after start of dosing up to Month 6						Biweekly ( $\pm 3$ days) until termination from the study					
Blood chemistry 	X		X		X			X			X			X
DNA testing (if applicable) 	X													
Urinalysis 	X													X
Serology 	X													
Physical examination 	X		X		X			X			X			X
Vital signs 	X	X	X	X	X	X	X	X	X	X	X	X	X	X
Height 		X	X	X	X	X	X	X	X	X	X	X	X	X
Weight		X	X	X	X	X	X	X	X	X	X	X	X	X
Labile plasma iron 	X	X	X	X	X	X	X	X	X	X	X	X	X	X
Transferrin saturation 	X	X	X	X	X	X	X	X	X	X	X	X	X	X
Serum ferritin 	X	X	X	X	X	X	X	X	X	X	X	X	X	X
Prolactin 		X												X

	Day -14 to 0 (Screening)	Month 0, Day 0 (Baseline)	Month 1 	Month 2	Month 3	Month 4	Month 5	Month 6	Month 7	Month 8	Month 9	Month 10	Month 11	Month 12 or End of Study 	
Dispense study medication		X	X	X	X	X	X	X	X	X	X	X	X		
Provide diary card		X	X	X	X	X	X	X	X	X	X	X	X		
Dosing	Three times daily from baseline until termination from the study														
Review and collect diary card			X	X	X	X	X	X	X	X	X	X	X	X	
Collect study medication containers			X	X	X	X	X	X	X	X	X	X	X	X	
Assess treatment compliance			X	X	X	X	X	X	X	X	X	X	X	X	
Prior & concomitant medications	X	X	X	X	X	X	X	X	X	X	X	X	X	X	
Medical events	X	X													
Adverse events		Throughout the study after start of dosing													
Transfusion history	Throughout the study														

**V:** Verify

-  Visits will be scheduled every 30 days ( $\pm$  10 days).
-  Patients will be terminated from the study at Month 12 or when they have been found to have a serum ferritin level  $\geq$  1000  $\mu$ g/L at 2 consecutive visits, whichever comes first.
-  Hematology: Hemoglobin, total WBC count, ANC, MCV, and platelet count.

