#### **Notes:**

- Since SF level may be impacted by the presence of infection, it must additionally be verified that the child has had no signs of infection in the previous 7 days, including the day of the visit, and that the level of CRP is no greater than 20% higher than the normal range for the patient's age. If there are signs of infection and/or the CRP level is above this threshold, the SF level must be checked again a minimum of one week later. (If an investigator has valid reason to believe that an SF level  $\geq 1000 \mu\text{g/L}$  may be attributable to infection even if this is not indicated by the CRP result, SF may be rechecked once more a minimum of one week later.)
- If a transfusion is scheduled on the day of the visit, the blood samples for serum ferritin, LPI, and TSAT must be collected before the transfusion is performed.
- Perform a physical examination (to be completed by the investigator or a qualified delegate)
- Measure vital signs (heart rate, blood pressure, and body temperature)
- Measure weight and height/length
- Review and update transfusion history
- Ask the parent/guardian (and patient, if applicable) about any adverse events that have occurred and concomitant medications that have been taken since the last site visit
- Additionally review the diary card for information on adverse events and use of concomitant medications, and file the diary card with the source documents
- Collect study medication containers, and check them in order to calculate treatment compliance

- Dispense enough study medication to last until the next scheduled visit, with an allowance for the visit window of  $\pm$  10 days, along with a reminder if necessary on how to administer it
- Administer the morning dose of study medication
- Provide the parent/guardian (or patient, if applicable) with a new diary card, along with a reminder if necessary about how to complete it
- Instruct parent/guardian (and patient, if applicable) to do the following:
  - Bring the patient to either the study site or a local laboratory for a weekly blood draw
  - In the event of any symptoms indicative of infection such as fever, sore throat, or flu-like symptoms, immediately interrupt therapy and contact the clinic
  - At the next site visit, bring back the completed diary card plus all medication containers, whether empty, partly used, or unopened

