## 7.2.1.8 Adverse Events of Special Interest

### 7.2.1.8.1 Neutropenia

Individuals taking deferiprone must be monitored for neutropenia, defined as a confirmed absolute neutrophil count (ANC) less than  $1.5 \times 10^9/L$ . Categories of neutropenia are as follows:

Mild neutropenia	A confirmed ANC < $1.5 \times 10^9/L$ but $\geq 1.0 \times 10^9/L$
Moderate neutropenia	A confirmed ANC < $1.0 \times 10^9/L$ but $\geq 0.5 \times 10^9/L$
Severe neutropenia / agranulocytosis	A confirmed ANC < $0.5 \times 10^9/L$

For a case of neutropenia to be confirmed, there must be 2 consecutive counts, a maximum of 3 days apart, that are both less than the specified value. If the 2 counts are not in the same severity category, a third count will be required to determine the severity. If a patient has just a single ANC value less than  $1.5 \times 10^9/L$ , this is to be documented in the CRF as an AE of “decreased ANC”, but is not to be defined as neutropenia. The investigator is to use judgment as to whether the decrease is clinically significant.

In addition to having ANC monitored, participants will be advised to immediately report any symptoms indicative of infection such as fever ( $\geq 38.0^{\circ}C$ ), sore throat, and flu-like symptoms at any time during the study and for one week following the last dose. They will be provided with an emergency services card with contact information, and advised to carry it with them at all times.

Depending on the severity of neutropenia, patients will either remain in or be withdrawn from the study. The management of different severities of neutropenia is described below.

**Mild neutropenia:** A patient who develops mild neutropenia is to interrupt treatment as soon as the neutropenia is confirmed, and ANC is to be monitored every 2 days until resolution.

The patient should re-initiate treatment once the event is resolved, defined as 2 consecutive  $ANC \geq 1.5 \times 10^9/L$ . If ANC is still  $< 1.5 \times 10^9/L$  after 14 days, the investigator is to do the following:

- Withdraw patient from the study and monitor him/her until resolution of the event
- Provide advice regarding protective isolation
- Examine patient the same day (if possible), including drug history and physical examination

- Notify ApoPharma Inc. using the SAE form

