**Moderate neutropenia:** A patient in whom a single ANC measurement  $<1.0 \times 10^9/L$  but  $\geq 0.5 \times 10^9/L$  is detected is to immediately stop treatment, without waiting for confirmation of the count, and a second measurement is to be done within 48 hours. If the second ANC is still  $< 1.0 \times 10^9/L$ , the investigator is to do the following:

- Withdraw patient permanently from the study and monitor ANC daily until resolution
- Provide advice regarding protective isolation
- Examine patient the same day (if possible), including drug history and physical examination
- Notify ApoPharma Inc. using the SAE form

**Severe neutropenia/agranulocytosis:** A patient in whom a single ANC measurement  $< 0.5 \times 10^9/L$  is detected is to immediately stop treatment, without waiting for confirmation of the count, and a second measurement is to be done within 48 hours. If the second ANC is still  $< 0.5 \times 10^9/L$ , the patient is to be permanently withdrawn from the study, and ANC is to be monitored daily until resolution. The following procedures should be done by the investigator or the treating physician, as appropriate:

- Provide protective isolation; if clinically indicated, admit patient to hospital and obtain vital signs every 4 hours
- Examine the patient the same day, if possible, including drug history and physical examination
- With the consent of the parent/guardian (or patient, if applicable), collect a blood sample to attempt to identify genetic or other biomarkers related to agranulocytosis
- Notify ApoPharma Inc. using the SAE form.

The following additional measures describe a suggested medical management and monitoring:

- If possible, consider obtaining bone marrow aspirate for:
  - Histology
  - Progenitor culture
  - Frozen storage (1 mL sample)
- If possible, consider obtaining bone marrow biopsy (minimum length 3 mm)

- Perform septic work-up including chest X-ray, blood, urine, and throat cultures
- Obtain q4h temperatures from patient (monitored by family at home if patient is not in the hospital)
- If warranted, administer granulocyte stimulating factors, such as G-CSF 10 µg/kg, on an in-patient basis if possible, beginning the same day that the ANC is confirmed as  $< 0.5 \times 10^9/L$ ; administer daily until ANC is  $> 1.5 \times 10^9/L$  on 2 consecutive days
- If ANC  $< 0.5 \times 10^9/L$  for 7 days, repeat bone marrow biopsy and aspirate weekly during the period of agranulocytosis, if warranted

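### The early termination visit for withdrawals other than at the ferritin threshold drops only prolactin from the Month 12 list, so as written it keeps the Month 12 dose for children already taken off drug

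*Protocol*

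**What the plan says.** Protocol Section 5.1 describes two kinds of early termination visit. Children who exit because ferritin reached 1000 µg/L at two consecutive visits follow an itemised list that ends with collecting the medication containers and contains no dose. For all other withdrawals there is no list, only a cross-reference: "the early termination visit will include all procedures done at the Month 12 visit except for measurement of prolactin".

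The Month 12 list, also in Section 5.1, includes this step: "Administer the final dose of study medication, ensuring that this is done at approximately the same time as at baseline". The prolactin draw 1.5 hours after the dose is the next item and is listed separately.

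Other parts of the protocol bear on whether a withdrawn child may be dosed:

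- Table 5.1, dosing row: "Three times daily from baseline until termination from the study".
- Section 4.5, on withdrawn patients: "All investigational product and materials should be returned". The same section has withdrawn patients come back for an early termination visit and makes no exception for neutropenia.
- Section 7.2.1.8.1: at a single neutrophil count below 1.0 × 10⁹/L (moderate or severe range), the patient "is to immediately stop treatment, without waiting for confirmation of the count".
- Section 4.5.2: a patient with moderate or severe neutropenia "is to be immediately withdrawn from the study". Mild neutropenia that has not resolved after 14 days also leads to withdrawal.
- Section 7.2.1.8.1, mild neutropenia: "The patient should re-initiate treatment once the event is resolved".
- Sections 4.5.2 and 7.2.1.8.2 stop drug for fever or any sign of infection, and Section 3.1 stops it for ferritin below the reference range for age.

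**The concern.** The cross-reference brings the whole Month 12 list into the exit visit and removes one item. Dosing is a different item, and nothing in the early termination text removes it. A coordinator working down the Month 12 list for a withdrawn child would therefore come to an instruction to give study drug.

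The children for whom this matters most are those withdrawn for neutropenia. Protocol Section 1.4 names severe neutropenia or agranulocytosis as the most serious adverse event associated with deferiprone, and the safety sections take these children off drug at once. A visit list should not say the opposite. What is at stake is the clarity of an operational safety instruction. No analysis depends on it.

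**Working it through.** The plan states no figure on this point and none can be derived, so the check is a comparison of texts.

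**1. What the cross-reference leaves in.** Take the Month 12 list and remove prolactin, both the pre-dose and the post-dose sample. What remains is haematology, blood chemistry, labile plasma iron, transferrin saturation, ferritin, C-reactive protein, urinalysis, physical examination, vital signs, weight and height, transfusion history, adverse events and concomitant medication, diary card, medication containers, and administration of the final dose. All of these suit an exit visit except the last.

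**2. Does the exception for prolactin cover the dose by implication?** Not on the wording. The exception is for a measurement, and giving drug is not a measurement. Nor is on-site dosing tied to prolactin in this protocol. Each visit from Month 1 to Month 11 includes "Administer the morning dose of study medication", and none of them has a prolactin sample. The Baseline Visit text also sets a general rule that the morning dose is given at the site on study visit days, which supports the literal reading.

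**3. Which rules does the leftover dose contradict?**

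| Group of withdrawn children | Rule contradicted |
|---|---|
| Every withdrawal covered by the clause | Table 5.1 ends dosing at termination. The Baseline Visit instructions place the early termination visit no later than one month after the last dose, so the last dose comes first. SAP Section 3.3 (COVID-19 remote visits) uses the same timing, within 30 days of the last dose. |
| Moderate or severe neutropenia | Also the immediate stop in Section 7.2.1.8.1 and the mandatory withdrawal in Sections 4.5 and 4.5.2. |
| Mild neutropenia unresolved at 14 days | Also the rule that treatment restarts only after resolution (Section 7.2.1.8.1) and the withdrawal rule in Section 4.5.2. If the count has recovered by the visit, the restart condition no longer bars a dose, but the withdrawal does. |
| Withdrawn for any reason while drug is on hold for fever or infection | Also Sections 4.5.2 and 7.2.1.8.2, until symptoms and the neutrophil count allow a restart. |
| Withdrawn for any reason while drug is on hold for low ferritin | Also Section 3.1, until ferritin has recovered. |

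**4. Was a dose intended?** The evidence says no. Dosing ends at termination, the visit is timed from the last dose, product is to be returned, and the itemised list for ferritin exits has no dose. That last item is weak support, because the ferritin-exit visit is a shorter visit in other ways too: it also omits labile plasma iron, transferrin saturation and ferritin.

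**5. Does anything correct the clause?** No. Section 7.2.2 also carries the End of Study procedures over to the early termination visit, in the context of laboratory samples, and it too says nothing about the dose. The passages in step 4 contradict the clause without amending it.

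**The case against.** The best defence is that the Month 12 dose exists for the sake of the prolactin test and so falls away with it. That step is worded differently from the routine dose of Months 1 to 11: it is called final, it is timed to match baseline, and its exact time is recorded. The only other visit list that asks for the dose time is baseline, which is also the only other visit with prolactin. A child already off drug has in any case had a final dose. Section 5 refers the reader to Table 5.1 for visit content, and that table shows dosing as a continuous row ending at termination and dispenses no drug at the last visit. A site reading the whole protocol, and especially the neutropenia rules, would withhold the dose.

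Most of this stands as an account of what was meant, and it is why the point is minor. It does not make the clause correct. The reader has to infer that a dose belongs to a measurement, at a visit type where the general rule is that the morning dose is given on site. The SAP also describes some visits in the past tense, so a notice to sites may now have limited practical use.

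A reader might infer that the protocol in effect directs sites to re-dose neutropenic children. The documents do not support that: the specific stop rules are explicit and would be expected to govern. A reader might also infer that the conflict with stop or interruption rules is confined to neutropenia. It is not, because drug is also withheld for fever, infection and low ferritin, and a child may be withdrawn during any of these.

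**Conclusion.** The clause is wrong as written, and the error is minor. Literally read, it keeps a dose at the exit visit for every withdrawal other than at the ferritin threshold, against the rules that end dosing at termination and time the visit from the last dose. The consequence would be most serious in children withdrawn for neutropenia. It also reaches any child withdrawn while drug is interrupted for fever, infection or low ferritin.

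A wrongful dose is unlikely, given the other passages. That is a judgement about how sites would read the protocol as a whole; the documents offer nothing from which to put a probability on it, and none is given. The primary and secondary endpoints, the sample size of 64 and the planned analyses are unaffected.

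**What to change.** In Protocol Section 5.1, Early termination visit, word the exception for other withdrawals as: *except for administration of study medication and measurement of prolactin*. Leave the Month 12 dose for completers as it is, since the 1.5-hour prolactin sample depends on it. If any child is still on study, send sites a short clarification; otherwise the correction serves the record and any later protocol that reuses this text. The cost is a few words in one sentence and, if needed, one site notice, with no effect on data or analysis.
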